# 5.4.2 HANDLING OF PARTICIPANT WITHDRAWALS OR TERMINATION

Withdrawn subjects will continue to be seen by their clinical audiologist and surgeon for regular follow-ups, but no additional data will be collected. Reasonable attempts will be made to resolve adverse events reported on withdrawn subjects. Subjects may voluntarily withdraw from the study at any time without fear of repercussion or loss of benefit from the study device.

When withdrawing, the subject should contact study personnel at their implanting site, who will contact the study monitor.

Reasons for withdrawal will be described in study reports as required. For subjects who are lost-to-follow-up, every effort will be made to determine the reason for non-compliance with study scheduling. A subject will be considered lost-to-follow-up (requiring withdrawal from the study) if that subject does not return to the clinical for six months or longer at one time. Appointments scheduled outside of the testing interval to the extent that the following interval will be impacted will result in consideration for withdrawal.

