#### 7.1.2 STUDY INTERVALS

- Enrollment/baseline
- Surgery (within 4 months of baseline)
- Cochlear implant activation (2-6 weeks post-operative)
- 1-month post-activation (3-6 weeks post-activation)
- 3-months post-activation (10-14 weeks post-activation)
- 6-months post-activation (20-28 weeks post-activation)
- 12-months post-activation (48 56 weeks post-activation)

Testing can occur outside of the provided window with prior approval from MED-EL.

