# 7.2.5 FOLLOW-UP INTERVALS

Follow-up testing will occur at 1 month, 3 months, 6 months, and 12 months post-activation. All testing should occur in a sound-treated booth under insert earphones or in the soundfield, with the subject seated one meter from the speaker. Speaker output should be calibrated prior to conducting study-related testing to ensure consistency across clinical trial sites. During soundfield measures, the contralateral ear should be plugged or masked as needed.

All testing should occur with an ear-level processor and be completed prior to making programming changes to the subject's processors. Additionally, processor settings should be verified prior to testing, with testing conducted using the patient's preferred program position and preferred volume and sensitivity settings.

Follow-up intervals will include the outcome measures below, which are also listed in *Table 1*:

Unaided audiogram, insert earphones

- Pure-tone air conduction thresholds (125 8000 Hz)
- o Pure-tone bone conduction thresholds (500 4000 Hz)
- Aided speech testing in quiet, implant ear only, soundfield
  - o CNC Words in quiet at 60 Db SPL
  - o One list of 50 words will be presented to the implant ear at each interval
  - Lists will be randomized at each clinical trial site
  - o Contralateral ear plugged or masked, as needed
- Aided speech testing in noise, implant ear only, soundfield
  - Az Bio Sentences in noise at 60 Db SPL with an SNR of +10 Db
  - Speech and noise will be presented at 0° azimuth
  - Two lists of 20 sentences each will be presented to the implant ear at each interval
  - o Lists will be randomized at each clinical trial site
  - o Contralateral ear plugged or masked, as needed
- Aided speech testing in noise, "everyday listening condition," soundfield
  - o AzBio Sentences in noise at 60 Db SPL with an SNR of +10 Db
  - Speech and noise will be presented at 0° azimuth
  - Two lists of 20 sentences each will be presented in the "everyday listening condition" at each interval
  - Lists will be randomized at each clinical trial site
  - OPTIONAL: testing can also be completed with an SNR of +5 Db
- Subjective questionnaires
  - o APHAB
  - o SSQ

Programming should be completed according to the recommendations in *Appendix B*. A copy of the maps created in each processor should be sent to the MED-EL Study Monitor at the completion of each interval.

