#### 8.2 TIME PERIOD AND FREQUENCY FOR EVENT ASSESSMENT AND FOLLOW-UP

The occurrence of an adverse event may be brought to the attention of the investigator during study visits, interim visits, or phone conferences over the duration of the study. All adverse device effects will be reported on the Adverse Event Report Form CRF. Information to be collected on the Adverse Event Report Form CRF includes: event description, date of onset, time of onset, seriousness, relationship to the device, unexpectedness, and the date/time of resolution (if applicable). Adverse events will continue to be followed until reaching adequate resolution or stabilization.

Investigators should record all reportable events with start dates occurring any time after the IC is obtained. Any medical condition that is present at the enrollment/baseline evaluation will not be reported as an adverse event. If the subject's condition deteriorates at any time during the study, however, the event will be reported.

Adverse events recorded as intermittent or fluctuating require documentation of onset and duration of each episode. This will be in addition to the original onset date of the event. Aes should not be recorded as resolved unless the reported event is no longer present and is not expected to reoccur.

[figure not shown]

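### The six-month lost-to-follow-up rule in 5.4.2 does not exempt the scheduled gap between the 6- and 12-month visits, so compliant subjects can meet it

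*Combined protocol and SAP*

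**What the plan says.** Section 5.4.2 of the protocol states that a subject is "considered lost-to-follow-up (requiring withdrawal from the study) if that subject does not return to the clinical for six months or longer" at one time. For withdrawn subjects it says that clinical care continues "but no additional data will be collected", apart from attempts to resolve adverse events already reported. The sentence before the definition says that, for subjects lost to follow-up, "every effort will be made to determine the reason for non-compliance with study scheduling". The sentence after it says that appointments so far outside their interval that they affect the next one lead to consideration for withdrawal.

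Section 7.2.5 fixes the schedule: "Follow-up testing will occur at 1 month, 3 months, 6 months, and 12 months post-activation". Section 7.1.2 gives the windows: "6-months post-activation (20-28 weeks post-activation" for the 6-month visit, and 48 to "56 weeks post-activation" for the 12-month visit. Neither section, nor Table 1 in 7.2.6, places a visit between them.

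Two provisions could bring a subject back sooner. Section 7.1.2 adds: "Testing can occur outside of the provided window with prior approval from MED-EL". Section 8.2 says adverse events may come to light "during study visits, interim visits, or phone conferences over the duration of the study". Neither requires a clinic visit between months 6 and 12.

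**The concern.** The definition turns on time away from the clinic, not on a missed visit. In the last interval of the study the planned time away is itself about six months or more, so a subject who has done everything asked can satisfy the definition. The consequence attached to it is mandatory withdrawal, which is stricter than the consideration for withdrawal attached to out-of-interval appointments. Section 5.4.1 adds that lost-to-follow-up subjects are reported to the monitors at once and that a signed letter documents the withdrawal, so sites need a definition they can apply literally and in the same way.

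Applied as written, the rule would cost:

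- 12-month CNC and AzBio scores, which the individual listing in 10.4.10 names and which would be expected to feed the repeated-measures analysis in 10.4.11 (that section does not list its visits);
- new late adverse device effects, which 4.2.2 says are reported for the whole study;
- an accurate retention table under 10.4.5, because compliant subjects would be counted as lost.

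The co-primary endpoints and their last-observation-carried-forward rule concern the six-month visit, before this gap opens, and are not affected.

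**Working it through.** The plan gives no figure of its own on this point, so there is none to reproduce. The check is interval arithmetic on the visit windows.

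**Inputs.** Windows in weeks after activation, from 7.1.2: 1 month 3–6, 3 months 10–14, 6 months 20–28, 12 months 48–56. Surgery falls within 4 months of baseline, and activation 2–6 weeks after surgery. The threshold in 5.4.2 is six months: 182.625 / 7 = 26.09 weeks, or 26.0 weeks if taken as 182 days.

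**Step 1: in-window gaps.** Shortest gap = start of the next window − end of the previous one. Longest gap = end of the next window − start of the previous one.

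| Interval | Shortest (weeks) | Midpoints (weeks) | Longest (weeks) |
|---|---|---|---|
| Activation to 1 month | 3 | 4.5 | 6 |
| 1 to 3 months | 10 − 6 = 4 | 12 − 4.5 = 7.5 | 14 − 3 = 11 |
| 3 to 6 months | 20 − 14 = 6 | 24 − 12 = 12 | 28 − 10 = 18 |
| 6 to 12 months | 48 − 28 = 20 | 52 − 24 = 28 | 56 − 20 = 36 |

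Before activation, baseline to surgery is at most 4 × 30.4375 / 7 = 17.4 weeks, and surgery to activation at most 6 weeks. Only the 6-to-12-month interval can reach 26 weeks.

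**Step 2: comparison with the threshold.** At the window midpoints the gap exceeds six months by 28 − 26.09 = 1.9 weeks; at its longest, by 36 − 26.09 = 9.9 weeks. Visits at exactly 6 and 12 calendar months are 12 − 6 = 6 months apart, which already meets a rule of six months or more.

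**Step 3: how much of the 12-month window avoids the rule.** The threshold falls at the week of the 6-month visit + 26.09.

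| 6-month visit | Threshold week | Part of weeks 48–56 before it |
|---|---|---|
| Week 20 | 46.1 | none |
| Week 24 | 50.1 | 50.1 − 48 = 2.1 weeks |
| Week 28 | 54.1 | 54.1 − 48 = 6.1 weeks |

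A subject seen at or before week 48 − 26.09 = 21.9 has no in-window 12-month date that avoids the rule. For a visit at week 20, the 12-month visit would have to fall more than 48 − 46.1 = 1.9 weeks before its window opens, with sponsor approval, unless the subject came to the clinic in between.

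**Step 4: illustration only.** Suppose visit times are independent and uniform in both windows, with no interim returns. The gap is then 28 + T, where T is triangular on −8 to 8, and P(gap ≥ 26) = 1 − (8 − 2)² / (2 × 8²) = 1 − 36/128 = 0.719. With 26.09 weeks it is 1 − 6.09²/128 = 0.710. With triangular timing peaked at weeks 24 and 52 the share is about 0.79 to 0.80. The documents give no timing distribution, so these are not estimates of an expected loss.

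**The case against.** The best reply is that context already limits the rule. The preceding sentence treats lost subjects as people whose failure to keep the schedule needs explaining, and the following one concerns appointments outside their interval. The scheduling-related termination reasons in 5.4.1 point the same way. A subject who attends at week 52 has returned, and a reading that removes subjects for following the required schedule defeats that schedule. Nothing suggests that a site would apply the rule this way.

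Much of this stands as evidence of intent: off-schedule subjects were probably the target. It does not cure the text. The preceding sentence says what to do about subjects already classed as lost; the next one defines the class and contains no schedule condition.

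A second reply is that the trigger is not returning to the clinic at all, and that 5.4.2 and 8.2 presuppose routine or interim visits. This also stands in part. Such visits would reset the clock, and because their frequency is not stated, no percentage of affected subjects can be supported. But the regular follow-ups in 5.4.2 are described for subjects already withdrawn, and 8.2 mentions interim visits only as one way an event may come to light. Keeping on-schedule subjects in the study should not depend on visits that the protocol does not require.

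Finally, the consequences are modest: secondary endpoints are descriptive, and events already reported are still followed. That is accepted, and it limits the severity.

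**Conclusion.** The concern holds, as a minor point. Sections 5.4.2 and 7.1.2 are inconsistent as written: in-window gaps between the 6- and 12-month visits run from 20 to 36 weeks against a threshold of about 26, so fully compliant subjects can meet a definition that requires their withdrawal. The problem is confined to this one interval. The conclusion rests only on the stated windows and on six months being about 26 weeks. Not every compliant subject is caught, since gaps of 20 to just under 26 weeks are also in window and any interim return resets the clock. How many would be caught cannot be determined from the documents; the 70–80% range is illustrative under the assumptions stated with it. What is at risk is 12-month data, capture of new late adverse device effects and the accuracy of the retention count. The primary analysis is not at risk.

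**What to change.** State in 5.4.2 that an on-schedule gap between the 6- and 12-month visits does not count as loss to follow-up. One way is to keep the six-month period and add the condition that a scheduled visit has been missed after its window, or its sponsor-approved extension, has closed.

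The condition is better added to the six-month period than put in its place. A subject who misses only the 3-month visit is away at most 28 − 3 = 25 weeks with the other visits in window, and is not lost under the present rule; a missed-visit test alone would change that. The combined rule still works at the end of the study: a subject last seen in the 6-month window who has not returned when the 12-month window closes has been away at least 56 − 28 = 28 weeks.

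The cost is one clause in 5.4.2, with no extra visits, subjects or analyses.

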# 6 STUDY DEVICE

#### 6.1 STUDY DEVICE DESCRIPTION

# 6.1.1 CLASSIFICATION

This clinical trial is intended to change indications on a currently-approved, class III medical device.

#### 6.1.2 DETAILS OF MANUFACTURER

The device is manufactured by MED-EL Elektromedinische Geraete GmbH. MED-EL Corporation is the US importer and the sponsor of this clinical trial.

#### 6.1.3 GENERAL DESCRIPTION

The MED-EL SYNCHRONY/SYNCHRONY 2 Cochlear Implant System is a currently FDA-approved cochlear implant system consisting of the MED-EL SYNCHRONY/SYNCHRONY PIN or SYNCHRONY 2/SYNCHRONY 2 PIN Cochlear Implant, SONNET/SONNET 2 (EAS) processor, the MAX programming interface, and the surgical kit. The implanted portion, the MED-EL SYNCHRONY implant, is surgically implanted under the skin behind the ear. It consists of a titanium housing and an active electrode array that is inserted into the cochlea during surgery. The MED-EL SYNCHRONY PIN is a variant of the MED-EL SYNCHRONY which has two pins on the bottom of the implant stimulator housing for fixation.

Various active electrode arrays are available as part of the MED-EL SYNCHRONY series of Cochlear Implants. Included in this clinical trial will be the SYNCHRONY +FLEXSOFT and SYNCHRONY +FLEX. The SYNCHRONY +FLEXSOFT is intended to be used in open cochleae (no obliteration or ossification) for an electrode insertion depth of about 31 mm. The SYNCHRONY +FLEX is intended to be used in open cochleae (no obliteration or ossification) for an electrode insertion depth of about 28 mm.The +FLEX and +FLEXSOFT electrodes are currently approved by the FDA.

The Patient Kit consists of two Audio Processors (SONNET EAS/SONNET 2 EAS/RONDO/RONDO 2/RONDO 3) and related accessories, chosen in various combinations by the subject. Each subject must select at least one SONNET EAS/SONNET 2 EAS processor in their patient kit configuration. The FDA-approved SONNET EAS and SONNET 2 EAS Audio Processors include a modular design, and can be worn entirely at ear level. SONNET/SONNET 2 (EAS) is a variant of the also FDA-approved SONNET/SONNET 2 Audio Processors — both contain the same components, with the addition of an acoustic unit in the EAS variant. SONNET EAS and SONNET 2 EAS also require use of an acoustic ear hook, upon which an earmold can be attached. The SONNET/SONNET 2 (EAS) Audio Processors use the FDA-approved DL-coil to transmit the signal across the skin. RONDO/RONDO 2/RONDO 3 are single-unit audio processors worn on the head at the location of the implant. MED-EL's MAESTRO System software must be used to program the SONNET EAS/SONNET 2 EAS and RONDO/RONDO 2/RONDO 3 Audio Processors.

The acoustic unit of the EAS variant is intended for use by patients with functional low-frequency hearing. Post-operative acoustic amplification (combined electric-acoustic stimulation) is indicated for hearing losses between 30 dB HL and 80 dB HL in the frequency range between 125 and 1700 Hz. Subjects who do not have post-operative unaided thresholds between 30 dB HL and 80 dB HL will use the SONNET EAS/SONNET 2 EAS processor without the acoustic unit enabled. Without the acoustic unit enabled, the SONNET EAS/SONNET 2 EAS processor will have the same performance as the also FDA-approved SONNET/SONNET 2 Audio Processor.

Subjects will be fit using the FDA-approved MAESTRO System Software. Programming will be completed using the approved Fine Structure coding strategies, as well as Automatic Sound Management (ASM) 2.0. ASM 2.0 includes the use of two front-end noise reduction features for the microphones' signal path. First, microphone directionality that is able to operate in an Omnidirectional, Natural, or Adaptive Mode. Secondly, a wind noise reduction algorithm that will reduce wind noise picked up by the microphones.

#### 6.2 STUDY DEVICE CONTROL

# 6.2.1 ACQUISITION

MED-EL SYNCHRONY/SYNCHRONY 2 Cochlear Implant System and audio processors will be sent to clinical trial sites from MED-EL Corporation. Devices will be ordered by the clinical trial site and processed and shipped according to relevant SOPs at MED-EL. A primary and a back-up cochlear implant will be provided for each subject. Devices will not be shipped until the proper documentation from enrollment/baseline testing has been received.

# 6.2.2 LABELING

Packaging will be affixed with a label stating: "CAUTION - Investigational Device. Limited by Federal (or United States) law to investigational use." Both the primary and back-up cochlear

implants will be labeled for investigational use only. The patient kit will also be labeled accordingly.

#### 6.2.3 STORAGE

All devices related to the study will be stored separately from approved cochlear implant systems not involved in the clinical trial. There are no additional requirements for storage of the device.

#### 6.2.4 ACCOUNTABILITY

MED-EL will be responsible for creating and storing records related to device accountability and traceability. Records of shipment, including the name and address of the investigative site, subject ID, device information, date of shipment, and serial numbers, will be stored at MED-EL according to the relevant SOPs. Devices returned to MED-EL as unused back-up devices or repairs will be properly documented and stored. Implants requiring explantation will be reported to FDA and documented according to internal procedures.

# 7 STUDY PROCEDURES AND SCHEDULE

#### 7.1 STUDY PROCEDURES

## 7.1.1 STUDY SPECIFIC PROCEDURES

The following procedures will be performed over the duration of the study and will be documented for each subject enrolled in the study.

- Informed Consent (IC): Investigators will review the IC with potential subjects and obtain signature prior to initiating study activities.
- Medical Assessment: Subjects should be evaluated for their ability to undergo surgery. This
  should include a chart review to document prior surgeries and known health conditions, as
  well as ear-related history. All subjects should also undergo a complete otologic exam and
  radiologic assessment, for proof of patent cochleae, if this has not already been completed.
- Surgery: Cochlear implant surgery will be performed once a subject has consented to participating in the study and completed pre-operative assessment.
- Tympanometry: Middle ear function will be measured by the use of tympanometry to determine whether or not middle ear status disqualifies the subject from participation in the study.
- Unaided Thresholds: Unaided air conduction thresholds will be measured pre- and postoperatively. Bone conduction thresholds will also be measured in order to determine whether hearing loss is conductive or sensorineural.
- Monosyllabic Word Testing: CNC words in quiet will be administered at 60 dB SPL as the coprimary outcome measure. Word testing will occur in the aided condition, either with

hearing aids (preoperatively) or the cochlear implant (postoperatively). One list will be presented per condition.

- Sentence Testing (implanted ear): AzBio sentences in noise will be administered at 60 dB SPL with a signal-to-noise ratio of +10 dB SNR. as the co-primary outcome measure. Sentence testing will occur in the aided condition, either with hearing aids (preoperatively) or the cochlear implant (postoperatively). Two lists will be presented per condition.
- Sentence Testing (both ears): AzBio sentences will be administered at 60 dB SPL with a signal-to-noise ratio of +10 dB SNR. Sentence testing will occur in the aided condition, either with hearing aids, the cochlear implant, or both. Two lists will be presented per condition. (OPTIONAL: time permitting, testing can also be completed with a signal-to-noise ratio of +5 dB SNR.)
- Subjective Questionnaires: Subjects will complete the APHAB questionnaire (Cox & Alexander, 1995) and the SSQ (Gatehouse & Noble, 2004) pre-operatively and postoperatively.
- Cochlear Implant Mapping: Programming of the audio processor should occur at each interval after device activation. Documentation of programs will be sent to the MED-EL Study Monitor.
- Adverse Event Reporting: adverse events should be monitored throughout the duration of the study and reported within appropriate timeframes as required.

#### 7.1.2 STUDY INTERVALS

- Enrollment/baseline
- Surgery (within 4 months of baseline)
- Cochlear implant activation (2-6 weeks post-operative)
- 1-month post-activation (3-6 weeks post-activation)
- 3-months post-activation (10-14 weeks post-activation)
- 6-months post-activation (20-28 weeks post-activation)
- 12-months post-activation (48 56 weeks post-activation)

Testing can occur outside of the provided window with prior approval from MED-EL.

# 7.2 STUDY SCHEDULE

# 7.2.1 POTENTIAL SUBJECT IDENTIFICATION

Before completing any enrollment activities, medical and audiological charts should be reviewed for potential subjects. Subjects who appear to be suitable candidates for the study should have the testing set forth in Section 7.2.2 completed.

# 7.2.2 ENROLLMENT/BASELINE

Prior to completing any candidacy or baseline testing, subjects will sign an IC form.

All testing should occur in a sound-treated booth under insert earphones or in the soundfield with the subject seated one meter from the speaker, depending on the test condition. Speaker output should be calibrated prior to conducting study-related testing to ensure consistency across clinical trial sites. During soundfield measures, the contralateral ear should be plugged or masked, as needed, except when testing is completed in the bilateral condition.

Baseline testing will include the following outcome measures:

- Tympanometry
- Unaided audiogram, insert earphones
  - o Pure-tone air conduction thresholds (125 8000 Hz)
  - o Pure-tone bone conduction thresholds (500 4000 Hz)
- Individual ear, aided speech testing in quiet, soundfield
  - CNC Words in quiet at 60 dB SPL
  - One list of 50 words will be presented to each ear individually
  - Lists will be randomized at each clinical trial site
  - Contralateral ear plugged or masked, as needed
- Individual ear, aided speech testing in noise, soundfield
  - o Az Bio Sentences in noise at 60 dB SPL with an SNR of +10 dB
  - Speech and noise will be presented at 0° azimuth
  - o Two lists of 20 sentences each will be presented to the implant ear only
  - o Lists will be randomized at each clinical trial site
  - Contralateral ear plugged or masked, as needed
- Bilateral, aided speech testing in noise, soundfield
  - o AzBio Sentences in noise at 60 dB SPL with an SNR of +10 dB
  - Speech and noise will be presented at 0° azimuth
  - Two lists of 20 sentences each will be presented
  - Lists will be randomized at each clinical trial site
  - OPTIONAL: testing can also be completed with an SNR of +5 dB
- Subjective questionnaires
  - o APHAB
  - o SSQ

This documentation should be received by the MED-EL Study Monitor before MED-EL will ship the investigational device.

At the baseline interval, an earmold impression should also be taken if the following criteria are met:

- The subject does not currently have a well-fitting earmold
- Unaided thresholds at 125 1000 Hz are 80 dB HL or better in the ear to be implanted

Surgery will be completed within four months of the above pre-op testing. If surgery is not completed within four months of baseline testing, the testing should be repeated to ensure accuracy. A soft surgery technique will be followed for all subjects. The surgical steps to be followed are drawn from the MED-EL Surgical Guide. These same steps are also detailed in *Appendix A*.

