#### 4.2 STUDY ENDPOINTS

#### 4.2.1 PRIMARY ENDPOINTS

The co-primary endpoint will be the comparison of CNC word score with the cochlear implant at six months post-activation to the pre-operative aided CNC word score in the implanted ear. Improvement will be defined as equal to or greater than 10 percentage points. Testing will occur in the soundfield at 60 dB SPL. The second co-primary endpoint will be the comparison of AzBio sentence score in noise with the cochlear implant at six months post-activation to the pre-operative aided AzBio score in the implanted ear. Improvement will be defined as equal to or greater then 10 percentage points. Testing will occur in the soundfield at 60 dB SPL with a signal-to-noise ratio of +10 dB SNR.

Study success will be determined based on the analysis of both co-primary endpoints. In order for the study to be considered successful, both co-primary endpoints must be met.

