#### 5 STUDY ENROLLMENT AND WITHDRAWAL

#### 5.1 PARTICIPANT INCLUSION CRITERIA

Individuals must meet all of the inclusion criteria set forth below in order to qualify for inclusion in this study.

- Adults, 18 years of age or older at the time of implantation
- Moderate to profound hearing loss in the low frequencies and severe to profound hearing loss in the high frequencies, bilaterally as defined by (see *Figure 1* below for example audiogram information)
  - o Low-frequency PTA (250, 500, and 1000 Hz) greater than 40 dB
  - High-frequencies not better than 65 dB (3000 Hz 8000 Hz)
- Sensorineural hearing loss, demonstrated by an air-bone gap of less than or equal to 10 dB
- Limited benefit from appropriately fit hearing aids, defined by CNC word score in quiet of 60% or less in the ear to be implanted and 70% or less in the non-implanted ear
- CNC word score in quiet of greater than or equal to 10% in the ear to be implanted
- Evidence of appropriately fit hearing aids as determined by the audiologist
  - Bilateral hearing aids should be considered standard of care, except in situations where the audiologist, physician, or potential subject determines that unilateral fit is optimal

- Hearing aid fit should be verified through accepted measures such as functional gain or real-ear verification
- If appropriately fit hearing aids have not been worn within the last year, a 30day hearing aid trial must be completed prior to enrollment in the study
- Fluent in English
- No radiological contraindications
- Ability to undergo general anesthesia
- Appropriate motivation and expectation levels
- Stated willingness to comply with all study procedures for the duration of the study

[figure not shown]

FIGURE 1 – Example inclusion audiogram showing audiometric threshold criteria. NOTE: Subjects may fall outside of the shaded area but still meet the PTA criteria.

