# 10.7 MEASURES TO MINIMIZE BIAS

Because this is a one-arm trial with all subjects receiving the same treatment, measures to minimize bias in the form of randomization and blinding are not relevant. However, one form of bias control implemented in this trial is that the presentation order of the CNC word lists is randomized at each follow up visit.

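### One 50-word CNC list both decides entry and serves as the baseline for the co-primary CNC change, so regression to the mean enters the estimate, with a net direction that depends on the candidate pool

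*Combined protocol and SAP*

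**What the plan says.** Section 7.2.1 sends likely candidates straight to the baseline battery: "Subjects who appear to be suitable candidates for the study should have the testing set forth in Section 7.2.2 completed". Section 7.2.2 gives the CNC part of that battery as "One list of 50 words will be presented to each ear individually", and Table 1 shows one combined candidacy and pre-operative column.

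The resulting score has three uses:

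- **Entry.** Section 5.1 sets a ceiling, "CNC word score in quiet of 60% or less in the ear to be implanted and 70% or less in the non-implanted ear", and a floor, "CNC word score in quiet of greater than or equal to 10% in the ear to be implanted".
- **Score range.** Section 10.6 requires at least 10 subjects in each of 0-20%, 21-40% and 41-60%. With the floor, the lowest range is in effect 10-20%.
- **Baseline.** Section 4.2.1 defines the endpoint as the "comparison of CNC word score with the cochlear implant at six months post-activation to the pre-operative aided CNC word score", and Section 10.4.2 tests the mean change against 10.

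Repeat testing is foreseen only for delay: "If surgery is not completed within four months of baseline testing, the testing should be repeated to ensure accuracy". On bias, Section 10.7 says that "measures to minimize bias in the form of randomization and blinding are not relevant" and names randomised CNC list order as its one form of bias control.

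**The concern.** A 50-word list is a noisy measure of an ear's aided performance. When the same noisy score decides who enters and then serves as the comparator, the errors in the enrolled baselines need not average to zero. A later score, whose errors were not selected on, moves back toward the true value with no treatment effect. In a controlled trial this movement occurs in both arms and cancels. Here each subject is his or her own control, so it is counted as change with the implant. Randomising list order does not touch it.

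Two things are at stake: the size of the reported CNC change, with the error rate of its test near the margin, and any reading of change by baseline score.

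**Working it through.** **1. The plan's own figure, to settle which SD applies.** Inputs from Section 10.5: n = 50, one-sided alpha 0.025, margin 10, CNC change 24.4, SD 21.9, stated power about 90%. Power is 1 - F(t crit; 49 df, ncp), with t crit = 2.010 and ncp = (24.4 - 10) / (SD/√50).

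- SD of change 21.9: SE = 21.9/√50 = 3.10, ncp = 14.4/3.10 = 4.65, power 99.5%. This does not match.
- SD of change √2 × 21.9 = 31.0: SE = 4.38, ncp = 3.29, power 89.7%. This matches. The AzBio figure behaves the same way (98.5% against 83.1%; 83% stated).

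The protocol does not say which SD is meant, so both are carried below.

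**2. Noise in one list.** The binomial standard error is √(p(1-p)/50): 7.1 points at 50% correct and 6.9 points at 60%.

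**3. Selection at each limit.** With X ~ Binomial(50, p), entry needs 5 ≤ X ≤ 30.

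- True score 65%: enters with probability 0.27. True score 70%: 0.085. These are chance-low entries.
- True score 8%: enters with probability 0.37. This is a chance-high entry.

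**4. Net bias.** Bias = E[true score - observed score | 10% ≤ observed ≤ 60%]. True scores are assumed normal with SD 15-20; the pool means are assumptions.

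| Assumed pool mean | Net bias in CNC change (points) |
|---|---|
| 20 to 30 | -0.4 to +0.1 |
| 40 | +0.5 to +0.6 |
| 50 | +1.1 to +1.2 |
| 60 | +1.7 to +2.2 |

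If chart review has already screened on one independent 50-word score within the same limits (also an assumption), the 40-to-60 rows shrink to about +0.35 to +1.4. In the other direction, binomial noise is a minimum. With a beta-distributed pool of mean 50 and SD 20, adding session-to-session noise of SD 8 points raises the bias from +1.0 to +2.1.

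**5. Change by baseline score.** For pool means of 40 to 60, subjects observed at 10-20% carry a bias of about +3 to +7 points. At a pool mean of 40 the 41-60% range is biased by about -1.

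**6. Effect on the CNC test if the true gain is exactly 10.** P(reject) = 1 - F(2.010; 49 df, bias/SE).

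| Bias | SD of change 31.0 | SD of change 21.9 |
|---|---|---|
| 0 | 2.5% | 2.5% |
| 1 point | ncp 1/4.38 = 0.23, 4.1% | ncp 1/3.10 = 0.32, 5.0% |
| 2 points | ncp 2/4.38 = 0.46, 6.5% | ncp 2/3.10 = 0.65, 9.2% |

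**7. With the fix.** If the baseline is a second list whose error is independent of the first, the expected bias is 0.0 in every scenario. Averaging two lists and using the average for both purposes only about halves it (for example 1.0 to 0.5, or 2.1 to 1.1).

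**The case against.** The strongest reply is that the effect is small, of uncertain sign, and unlikely to decide the trial. Much of that stands. The floor works against the ceiling. The nearest mean CNC score in the protocol, 28.5% in a cited series of implanted adults (Section 2.1), is not this trial's pool, but a pool centred there would give a net bias near zero. Charts are reviewed before testing, which probably reduces the effect. The planned excess over the margin is 24.4 - 10 = 14.4 points, so even 2.2 points is about 15% of it. Success also requires AzBio, which has no entry cut-off. No planned test uses the Section 10.6 ranges.

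What does not stand is that the problem can therefore be left alone. Nothing in the documents estimates or removes the bias. The trial's purpose is to extend candidacy up to 60%, and Section 5.3 lets sites look for patients who previously did not qualify. A higher-scoring pool, with upward bias, is therefore plausible, though not established.

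Four stronger readings are tempting, and the documents do not support them:

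- **That the baseline is always biased low.** The 10% floor on the same score rules out an unconditional direction.
- **That the worse-scoring ear is implanted, which enlarges the bias.** No section says how the ear is chosen.
- **That ears truly above 60% fall outside the intended label.** Section 1 defines limited benefit by test scores, so an observed score of 60% or less is the indication.
- **That the tester's knowledge of the cut-off shifts the score.** The documents give nothing from which to show or size this, and a second list given by the same tester would not cure it.

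**Conclusion.** The point holds in conditional form. One list has both roles, there is no control, and regression to the mean therefore enters the co-primary CNC change. Its net size is roughly -0.4 to +2.2 points over the assumed normal pools, upward for pool means of about 40 or more and near zero or slightly negative at 30 or below. Chart screening would make it smaller and session noise larger. The result rests on assumed true-score distributions and on binomial list error.

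The 4.1-5.0% (1 point) and 6.5-9.2% (2 points) error rates apply to the CNC test alone, with the true gain exactly at the margin. A reader might take 9% as the trial's false-positive rate. It is not, because it needs a bias near the top of the range, the smaller SD, and an AzBio result that is otherwise sure to pass. The CNC estimate is more exposed than overall study success, and readings of change by baseline score are more exposed than either. This is an inexpensive improvement to the design; it does not overturn the trial.

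**What to change.** In Sections 7.1.1 and 7.2.2, add a second 50-word CNC list in the ear to be implanted at the pre-operative visit. Two AzBio lists per condition are already given.

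- Use the first list only for eligibility and the Section 10.6 range.
- Use the second list only as the baseline for the change score, whatever its value. Do not reapply the 10% and 60% limits to it, and do not average the two lists.
- Carry the same separation into the repeat testing after a four-month delay, and define the baseline accordingly in the SAP, which Section 10.1 says is still to be created.
- For subjects already enrolled on one list, keep that baseline, report results separately by baseline type as a sensitivity analysis, and state possible regression to the mean as a limitation.
- Do not treat chart CNC scores as an unbiased comparator. Section 7.2.1 uses the charts to pre-screen, so those scores may be selected too.

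**Cost.** A few minutes of testing in one ear with the same staff and equipment, and no change to n = 50. Baselines will be mixed if enrolment has begun, and the reported CNC change may be slightly smaller. A second list on the same day removes list error but not a good or bad day shared by both lists, so the SAP should state that remaining limit.
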